# 6.4.1.2 Secondary Efficacy Variables

Secondary efficacy endpoints include the following:

- Diagnostic performance (sensitivity, specificity, PPV and NPV) of different thresholds of quantitative and dynamic measures of lesion F-fluciclovine uptake versus SoT derived from central histopathological analysis of all lesions, at subject-level and lesion-level.
- Subject-level sensitivity, specificity, PPV and NPV of F-fluciclovine PET scan for detecting recurrent brain metastases, based on combined application of the established image interpretation criteria.
- Lesion-level sensitivity, specificity, PPV and NPV of F-fluciclovine PET for detecting recurrent brain metastases, based on combined application of the established image interpretation criteria.

# Dynamic measures of lesion F-fluciclovine uptake

Time activity curve (TAC) based on F-fluciclovine uptake of all sampled lesions, including the reference lesion, on dynamic imaging data will be derived from the following image acquisition frame sequences: first 10 min after injection - 12 frames of 5s, 6 frames of 10s, 6 frames of 30s and 5 frames of 60s; from 10 min to 30 min after injection – 5 minute acquisition frames.

- Type 0: absent uptake
- Type I: continuous increase in uptake throughout the study
- Type II: initial uptake followed by plateau later in the study
- Type III: relatively rapid uptake with reduction in uptake later in the study

For each TAC type, a 2x2 table will be created for subject level and also lesion level, for each reader. Each TAC type will be considered separately (eg. Type 0 vs Type I/II/III). In addition a combination will be evaluated: Type 0/I vs Type II/III.

	Tumor Present (SoT)	Tumor Absent (SoT)	
TAC Type X	True positive	False positive	
TAC Not Type X	False negative	True negative	

Sensitivity, specificity, PPV and NPV for each TAC type will be calculated in the same way as the primary endpoint.

Confidential Page 10 of 22

#### Quantitative analysis

Lesion(s) and background structures will be outlined visually on static imaging data (e.g., from 10-20 minutes post-injection), and the measures recorded will include:

- lesion maximum standardized uptake value (SUVmax),
- lesion peak standardized uptake value (SUVpeak),
- background mean standardized uptake value (SUVmean),
- maximum tumor: background ratio (TBRmax; tumor SUVmax: SUVmean background),
- peak tumor: background ratio ( $TBR_{peak}$ ; tumor  $SUV_{peak}$ : background  $SUV_{mean}$ ).

### 6.4.2 Description of Safety Variables

Safety will be assessed from the time of F-fluciclovine administration until 1 day post-F-fluciclovine administration based on reported serious and non-serious adverse events (SAEs and AEs, respectively).

Vital signs, concomitant medications, and pregnancy test results will also be recorded.

#### 6.4.2.1 Adverse Events

An AE is any untoward medical occurrence in a clinical investigation subject administered a pharmaceutical product and that does not necessarily have a causal relationship with the treatment. An AE is therefore any unfavorable and unintended sign (including an abnormal laboratory finding), symptom or disease temporally associated with the administration of an investigational product, whether or not related to that investigational product. An unexpected AE is one of a type not identified in nature, severity, or frequency in the current Investigator's Brochure or is of greater severity or frequency than expected based on the information in the Investigator's Brochure.

The investigator will probe, via discussion with the subject, for the occurrence of AEs during each subject visit within the AE collection period. The collection period for all AEs will begin after initiation of F-fluciclovine injection and end 1 day post-F-fluciclovine administration (ie. Day 2). Any unresolved AE at Visit 3 Safety Follow-up beyond Day 2 will be followed until resolution or stabilization. The investigator will record the information in the site's source documents. Adverse events will be recorded in the subject electronic Case Report form (eCRF). Adverse events will be described by duration (start and stop dates and times), severity, outcome, treatment and relation to study drug.

### 6.4.2.2 Vital Signs

Vital signs including body temperature, blood pressure, pulse and respirations will be collected at Visit 2 (IMP injection + PET) after resting for at least 5 minutes before IMP injection, and after resting for at least 5 minutes following PET scan. The vital signs should be collected between 5 to 60 minutes before and after the PET scan.

Confidential Page 11 of 22

#### 6.4.2.3 Concomitant Medication

All concomitant medication and concurrent therapies will be documented at Screening (Visit 1), at IMP administration (Visit 2) and at the 2-day post-treatment Safety Follow-up phone call (Visit 3), and at early termination when applicable. Dose, route, frequency of administration, and indication for administration and dates of medication will be captured.

### 6.4.2.4 Laboratory Parameters

A human chorionic gonadotropin (HCG) urine pregnancy test will be obtained from female subjects who are of childbearing age prior to their participation in the study at Screening, and again on Visit 2 before IMP administration (or on day prior to IMP administration).

### 6.5 Data Quality Assurance

Report summaries will be generated using validated Base SAS® software, version 9.4 or higher, on a PC or server-based platform. Additional validated software may be used to generate analyses, as needed.

All SAS programs that create outputs or supporting analysis datasets will be validated by a second statistical programmer or biostatistician. At a minimum, validation of programs will consist of a review of the program log, review of output or dataset format and structure, and independent confirmatory programming to verify output results or dataset content. Additionally, all outputs will undergo a review by a senior level team member before finalization.

The content of the source data will be reviewed on an ongoing basis by project statistical programmers and statisticians. Data will be checked for missing values, invalid records, and extreme outliers through defensive programming applications, analysis-based edit checks, and other programmatic testing procedures. All findings will be forwarded to the project data manager for appropriate action and resolution.

#### 7 STATISTICAL METHODS

#### 7.1 General Methodology

Data will be analyzed by Precision for Medicine biostatistics personnel. Statistical analyses will be reported with tables, figures, and listings, presented in rich text format, and using recommended ICH numbering. Output specifications for all tables, figures, and listings will be in conformance with guidelines specified by the ICH in Appendix 7 of the *Electronic Common Technical Document Specification* (Apr 2003).

#### 7.1.1 Reporting Conventions

Tables and figures will be summarized for all subjects in the specified analysis set. In general, all data collected and any derived data will be presented in subject data listings, for all enrolled subjects. Listings will be ordered by subject number, and assessment or event date.

Confidential Page 12 of 22

In general, continuous variables will be summarized to indicate the study population sample size (N), number of subjects with available data (n), mean, SD, median, minimum, and maximum values. Categorical variables will be summarized by the population size (N), number of subjects with available data (n), number of subjects in each category, and the percentage of subjects in each category. Unless otherwise noted, the denominator to determine the percentage of subjects in each category will be based on the number of subjects in the specified analysis set.

Non-zero percentages will be rounded to one decimal place. Rounding conventions for presentation of summary statistics will be based on the precision of the variable of summarization, as it is collected in its rawest form (i.e., on the eCRF) or as provided within an external file) and are outlined as follows:

- The mean and median will be rounded to one more decimal place than the precision of the variable of summarization;
- Standard deviation will be rounded to two more decimal places than the precision of the variable of summarization; and
- Minimum and maximum values will be presented using the same precision as the variable of summarization.

Other statistics (e.g., CIs) will be presented using the same general rules outlined above, or assessed for the most appropriate presentation based on the underlying data.

#### 7.1.2 Standard Calculations

Where appropriate, the calculated study day of each assessment or event will be presented with the assessment or event date on subject data listings, where study day will be determined as:

- The assessment/event date minus the date of IMP, if the assessment/event date is prior to the date of IMP; and
- The assessment/event date minus the date of IMP, plus one, if the assessment/event date is on or after the date of IMP.

#### 7.2 Analysis Sets

The Full Analysis Set (FAS) will include all enrolled subjects dosed with IMP, with an evaluable Visit 2 on-study PET scan.

The Safety Analysis Set (SAF) will be used for all safety analyses, and will include all subjects who have been dosed with IMP (with or without the associated PET scan).

The Imaging Evaluable Analysis Set (IEAS) includes all subjects who have been dosed with IMP, have an evaluable Visit 2 on-study PET scan, and an evaluable central histopathology report (defined in the Histopathology Charter) from the sample obtained from the Visit 4 SoC craniotomy.

Confidential Page 13 of 22

#### 7.3 Study Subjects

# 7.3.1 Disposition of Subjects

Subject disposition will be summarized for all subjects who entered the study, by study site and overall. Summaries will include the number of subjects enrolled, failed/completed screening, and the number and percentage of subjects in each analysis set, completing the study, and discontinuing the study early by the primary reason for discontinuation. Withdrawals relating to coronavirus disease of 2019 (COVID-19) will be included.

#### 7.3.2 Protocol Deviations

Deviations from the protocol, including those specifically relating to COVID-19, and relevant details will be tracked throughout the study and listed. Critical and major deviations will be summarized for the full analysis set, by study site and overall.

#### 7.3.3 Demographic and Other Baseline Characteristics

Demographic variables including age, sex, ethnicity and race will be summarized for the FAS, SAF and IEAS. Age will be as recorded on the eCRF and will not be recalculated.

Age will be summarized using descriptive statistics, and age group (<65 years old, ≥65 years old). Sex, ethnicity, and race will be summarized with the number and percentage of subjects in each parameter category.

Baseline characteristics include height, weight, body mass index (BMI), Eastern cooperative oncology group (ECOG) performance status, medical history, and prior treatment history. BMI will be calculated as: weight (kg) / [height (cm) / 100]. Height, weight, BMI and ECOG will be summarized for the FAS, SAF, and IEAS; prior treatment history and medical history will be summarized for the FAS only. Height, weight, and BMI at baseline will be summarized using descriptive statistics. ECOG performance status will be summarized with the number and percentage of subjects with each score (0 to 4).

Primary tumor origin and the corresponding details such as disease staging and molecular profiles, where applicable, will be summarized, along with the extra-cranial (systemic) disease status and time since first known date of diagnosis of brain metastasis(es). Primary tumor origin will be categorized as Lung Cancer (non-small cell lung cancer [NSCLC] + small cell lung cancer [SCLC]), NSCLC, SCLC, Breast Cancer, Melanoma, and Other (colorectal, pancreatic, kidney, testes, cervix, ovary, head & neck, osteosarcoma, thyroid, other). Time (months) since first known date of diagnosis will be calculated as (screening date – first known date of diagnosis of brain metastasis(es))/30.4375. If the date of diagnosis is a partial date and day is not available, then day will be imputed as the 15th of the month for the purpose of the calculation. If day and month are both not available then the 1st July will be imputed.

Prior cancer treatments for primary tumor will be summarized with the number and percentage of subjects in each of the following categories:

Surgery

Confidential Page 14 of 22

- Lymph nodes dissection
- Radiotherapy
- Other ablative techniques
- Drug therapy

For the drug therapy category, each drug will be coded using the World Health Organization drug dictionary, WHODrug Global B3 Mar. 1, 2020, grouped into one of the following categories and summarized along with preferred term. The grouped categories will be provided for analysis by a medical expert:

- Chemotherapy
- Immunotherapy
- Targeted Therapy
- Other Therapy

Similarly, concomitant cancer treatments for primary tumor will be summarized by type of treatment (Chemotherapy, Immunotherapy, Targeted Therapy, Other Therapy) and preferred term. The data will come from the Concomitant Medication and Cancer Drug Therapies page, and will include data with the indication for "Treatment for Primary Cancer".

For prior therapies for brain lesions considered as equivocal (i.e. study lesions), the number and percentage of subjects with the following radiotherapies will be summarized:

- Stereotactic radiosurgery
- Whole brain radiotherapy
- Prophylactic cranial irradiation
- Other

The number of lesions (reference lesions and MRI surgical lesions) that have undergone stereotactic radiosurgery will also be counted. The number of subjects and lesions that have undergone laser interstitial thermal therapy (LITT) will be counted.

The number and percentage of subjects with other prior therapies for any non-study lesions, will be summarized using the following categories:

- Craniotomy
- Laser interstitial thermal therapy
- Stereotactic radiosurgery
- Whole brain radiotherapy
- Prophylactic cranial irradiation
- Other

Medical history terms on case report forms will be mapped to preferred terms and system organ classes using the Medical Dictionary for Regulatory Activities

Confidential Page 15 of 22

(MedDRA, version 23.0) and will be summarized by system organ class and preferred term. Medical history data will be listed and include start date, end date, ongoing at study start, preferred term and system organ class.

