#### **6 INVESTIGATIONAL PLAN**

#### 6.1 Overall Study Design

This is a prospective, open label, single arm, single dose study in subjects with solid tumor brain metastases previously treated with radiation therapy, designed to define

Confidential Page 5 of 22

image interpretation criteria for F-fluciclovine PET in detecting recurrent brain metastases (when read with standard magnetic resonance imaging (MRI) for anatomical reference).

Subjects with a history of brain metastases previously treated with primary, adjuvant or repeat (salvage) radiation therapy, with a recent standard of care (SoC) brain MRI found to be equivocal for recurrent brain metastasis, and who meet all inclusion criteria and none of the exclusion criteria, will be consented and enrolled. Sites are encouraged to enroll subjects with a variety of primary tumor types. In order to ensure variation in tumor types on the study population, the number of subjects with lung cancer will be capped at approximately 60% of enrolled subjects.

On-site investigators will prospectively annotate and measure the 'reference lesion' on a post-radiation treatment MRI scan and on the SoC MRI brain scan to confirm eligibility. The 'reference lesion' is defined as the lesion which is:

- equivocal for recurrent metastasis on SoC MRI (according to inclusion criterion #7, protocol section 6.2);
- intended for pre-planned SoC craniotomy; and
- if >1 equivocal lesion is intended for resection, the largest of these lesions.

If >1 equivocal lesion is intended for resection, the on-site investigator will also annotate and measure the other lesions (termed 'MRI surgical lesions') on the SoC MRI brain scan, defined by the same radiological criteria for a reference lesion per inclusion criterion #7 (see protocol section 6.2).

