#### 6.3.2 Method of Assigning Subjects to Treatment Groups

Not applicable. All subjects will receive a single dose of F-fluciclovine.

Confidential Page 8 of 22

\*\*Standard of care.\*\*

\*\*Demographic information recorded at Screening will include age, sex, race and ethnicity.

\*\*Baseline assessments will include pre-scan body weight and height.

\*\*Treatment history for previous cancer to include previous treatments for brain metastases and previous cancer treatments for primary tumor

\*\*A standard of care ECOG assessment may be recorded as the Screening ECOG if the assessment was performed within 28 days of Screening.

\*\*Vital signs (body temperature, blood pressure, pulse and respirations) will be collected after resting for at least 5 minutes before IMP injection, and after resting for at least 5 minutes following PET scan.

Females of child-bearing potential.

Eligibility review to include collection and review of prior pre- and post-treatment MRI brain scans as needed to confirm eligibility. Prior pre- and post-treatment MRI brain

seans and current SoC MRI images to be uploaded to central imaging core lab.

Additional PET lesions' are potential additional lesions identified by the on-site investigator on F-fluciclovine PET scan (with Visit 2 MRI for anatomical reference), not previously reported on SoC MRI, should be judged suggestive of brain metastasis, warranting confirmation according to SoC practice, and be neurosurgically feasible and accordingly, planned for biopsy / resection.

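### The partial-date rules for diagnosis of brain metastases have no upper bound, so time since diagnosis can be negative or too short (minor; one descriptive baseline row)

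*SAP*

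**What the plan says.** All of the rule is in SAP Section 7.3.3.

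- **Formula.** Time in months is "screening date – first known date of diagnosis of brain metastasis(es))/30.4375".
- **Day missing.** The text is "then day will be imputed as the 15", meaning the 15th of the recorded month.
- **Day and month missing.** "If day and month are both not available then the" 1st of July is imputed.

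No further condition is attached to either imputation.

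Two other places matter. Section 6.1 describes the population as "Subjects with a history of brain metastases previously treated with primary, adjuvant or repeat (salvage) radiation therapy", with a recent equivocal MRI as well. Section 7.1.1 says that continuous variables are summarized with "mean, SD, median, minimum, and maximum values".

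**The concern.** In this population diagnosis comes first, then radiotherapy for the metastases, then the equivocal MRI and enrollment. A true time since diagnosis therefore cannot be negative, and a true diagnosis date cannot follow the radiotherapy given for it. A fixed mid-year date that is not compared with any known later date can break both orderings.

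This is a stated rule that yields a wrong value when followed exactly, not a detail left to another document. Elsewhere the SAP does use a known date when it handles partial dates. Section 7.5.6 compares partial medication dates with the dosing date, and Section 7.5.2 uses the available date entries to judge whether an event began before dosing. The diagnosis rule makes no such comparison.

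What is at stake is the credibility of one baseline row. Because the minimum is printed, a single affected subject would show as an impossible value. Otherwise someone would have to improvise a correction after seeing the data, and Section 4 says the SAP exists to avoid post hoc decisions.

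**Working it through.** The SAP gives no figure on this point to reproduce. The check applies its own formula.

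**Inputs.** The formula and both imputation rules come from Section 7.3.3, and the order of events from Section 6.1. Planned enrollment is up to 40 (Section 7.6). Assumption: a non-leap year.

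**1. Year-only date, diagnosis in the screening year.** Months = (screening date - 1 July) / 30.4375.

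| Screening date | Days | Months |
|---|---|---|
| 15 March | -108 | -108/30.4375 = -3.55 |
| 30 April | -62 | -2.04 |
| 31 May | -31 | -1.02 |
| 30 June | -1 | -0.03 |
| 1 July | 0 | 0.00 |
| 31 December | 183 | 6.01 |

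Every screening date before 1 July gives a negative value.

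**2. Year-only date, diagnosis in an earlier year.** The smallest possible value is for screening on 1 January after an imputed 1 July of the year before: 184/30.4375 = 6.05 months. No negative value arises.

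**3. Day-only date.** The imputed 15th can pass screening only if both fall in the same month. The arithmetic limit is screening on the 1st: -14/30.4375 = -0.46 months.

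**4. Imputed diagnosis after treatment.** This needs only that the metastases were irradiated before 1 July of the recorded diagnosis year, whatever the screening year. Take treatment on 15 March of the diagnosis year and screening on 15 March of the next.

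- Interval from the imputed date: 365 - 108 = 257 days, or 8.44 months.
- True interval: at least 365 days, or 11.99 months.
- The result is positive and looks plausible, but is at least 108 days (3.55 months) too short.

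**5. Effect on the mean.** For screening on 15 March, the longest possible true value with diagnosis in the same year is 73/30.4375 = 2.40 months. If the true value is 2 months, the error is 2 - (-3.55) = 5.55 months. Over 40 subjects that moves the mean by 5.55/40 = 0.14 month.

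**6. How often a negative value could occur.** The SAP gives no minimum gap from diagnosis to screening, so a range is shown. The shares are of all same-year diagnosis and screening date pairs, equally weighted, given a year-only date.

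| Minimum gap (days) | Negative / all pairs | Share |
|---|---|---|
| 0 | 16,471 / 66,795 | 24.7% |
| 60 | 7,381 / 46,665 | 15.8% |
| 90 | 4,186 / 37,950 | 11.0% |
| 120 | 1,891 / 30,135 | 6.3% |
| 180 | 1 / 17,205 | about 0% |

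**The case against.** The best defense is that the trigger is narrow. A negative value needs a year-only date, in the screening year, with screening before 1 July. A recent diagnosis is the kind least likely to be recorded by year alone, and radiotherapy and an equivocal MRI must fit in before screening. The SAP gives no reason to expect many year-only dates, and eligibility rules in the protocol may set a minimum gap. Section 6.5 also requires checks for invalid records and a senior review of outputs, and a negative minimum would be noticed.

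Most of this stands as to frequency, but it does not remove the error. A year-only date is a valid source record; the impossible value arises in the derivation, where Section 6.5 sets no limit. The short but positive intervals in step 4 would not stand out in review. The no-imputation statement in Section 7.4.5.1 sits under the efficacy evaluation and does not override an explicit baseline rule.

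A reader might infer four stronger things, none of which the SAP supports:

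- **That the value could reach -5.95 months, for screening on 1 January.** A subject diagnosed and irradiated before screening cannot have both behind them in a year that has just begun. The same reasoning makes the 14-day figure for the day-only rule an outer limit.
- **That any imputed date after radiotherapy gives a negative value.** Only a date after screening does.
- **That the whole summary is biased downward.** The interval is certain to be too short only where 1 July falls after treatment or screening. For other year-only dates, 1 July is an ordinary mid-year choice.
- **That any brain-directed treatment could serve as the bound.** Section 7.3.3 lists prophylactic cranial irradiation among prior therapies, and that can properly precede diagnosis of metastases.

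**Conclusion.** The point holds as a minor error in a stated rule. Both partial-date rules lack an upper bound. The year-only rule gives an impossible negative value when diagnosis and screening share a calendar year and screening precedes 1 July. It also understates the interval whenever treatment of the metastases came before 1 July of the recorded diagnosis year.

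The visible harm would be a negative minimum; the mean would barely move. No efficacy or safety analysis is planned on this variable. The conclusion rests on the order of events in Section 6.1 and on at least one affected partial date occurring, which the SAP cannot tell us.

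**What to change.** Add one condition to both partial-date rules in Section 7.3.3:

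- The imputed diagnosis date may not fall after the screening date. If it would, use the midpoint between the start of the known period (1 January, or day 1 of the month) and the screening date.
- Where a complete date of treatment given for diagnosed brain metastases is recorded within the known period, use that earlier date as the bound instead. Prophylactic cranial irradiation does not count.

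For a year-only date in the screening year, with the screening bound and the midpoint rounded down to a whole day:

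| Screening date | Imputed diagnosis | Months, bounded | Months, current rule |
|---|---|---|---|
| 15 March | 6 February | 37/30.4375 = 1.22 | -3.55 |
| 31 May | 17 March | 75/30.4375 = 2.46 | -1.02 |
| 30 June | 1 April | 90/30.4375 = 2.96 | -0.03 |

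The imputed date then cannot fall after screening.

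The cost is a sentence or two in the SAP and a small change to the derivation. The screening date is already in the formula, so the first bound needs no new data. The second depends on treatment dates being recorded. The footnotes to the Schedule of Assessments say "Treatment history for previous cancer to include previous treatments for brain metastases" but do not mention dates. If none are available, the screening bound alone still prevents negative values, but the too-short intervals in step 4 would remain.
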